10.0 Procedures Involved

*10.1 Provide a description of **all research procedures or activities** being performed and when they are performed once a subject is screened and determined to be eligible. Provide as much detail as possible.*

NOTE: This should serve as a blueprint for your study and include enough detail so that another investigator could pick up your protocol and replicate the research. For studies that have multiple or complex visits or procedures, consider the addition of a schedule of events table in in your response.

Response:

Study 2:

During the Stage 1b Randomized Controlled Trial of the active intervention, the first group session will focus on viewing each of 4 cue recognition training videos and the Interventionist will lead a discussion intended to highlight the risk cues in each of the videos. After the session, links and passwords will be sent via email to each participant for the online safe dating and safe drinking learning modules and participants will be asked to complete them prior to the second group session, which will take place about one week after the first session. This second group session will elicit feedback on the dating and drinking learning modules (e.g., length, ease of use, engagement, interest). The training videos will be viewed again individually and participants will engage in behavioral skills rehearsal of appropriate responses in paired role plays with feedback from the PI and Interventionist. During the behavioral rehearsal segment, the PI or Interventionist will engage the group in a discussion of emotional barriers to engaging in appropriate dating and drinking safety behaviors (e.g., "I feel bad for the guy", "He might get really mad, "I might miss out on being with a great guy") and strategies for overcoming these barriers. Adaptive emotion regulation strategies will include cognitive reappraisal, distress tolerance, mindfulness of current emotions, acceptance, and problem solving. Immediately following this session, the post-intervention measures, including feedback on the intervention content and process, will be completed. Following the in-person RPCW sessions, a debriefing will occur to ensure that women have an opportunity to discuss any emotional discomfort or distress with the interventionist. Women will receive \$30 for completion of the post-intervention measures.

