At the beginning of the first in-person session and at the end of the second in-person session, for both the RPCW active intervention and the HEC condition, three standardized instruments will be administered to participants. **Participants will be seated a minimum of 6 feet apart in the group session room and administered these instruments on an individual laptop with earphones to allow them privacy.** These include the Video Vignette Risk Perception Measure (VVRPM) which assesses women's standardized ability to assess sexual assault risk cues. The Adult Faces test from the Diagnostic Analysis of Nonverbal Accuracy 2 (DANVA2) which is used to measure an individual's general ability to sensitivity to perceive nonverbal cues, and the sDERS a measure used to assess state emotion regulation (assessed using a web-based platform as are the other survey measures for the study). All data will be uploaded off of these laptops and saved to the project UB Box at the end of each in-person session.

Outlines for the in-person RPCW and HEC sessions are attached and links to the on-line learning units for both the RPCW and HEC are included for review.

10.2 Describe what data will be collected.

NOTE: For studies with multiple data collection points or long-term follow up, consider the addition of a schedule or table in your response.

Response:

Study 2:

Participants will participate in the intervention over about one week. They will attend two in-person group intervention sessions about one week apart, and complete two on-line units during the intervening week. They will be asked to complete follow-up on-line assessment surveys at 3 months and 6 months post intervention.

The follow-up surveys will be administered online and are included for review.

 *10.3 List any instruments or measurement tools used to collect data (e.g. questionnaire, interview guide, validated instrument, data collection form).*

Include copies of these documents with your submission.

Response:

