Study 2 data collection instruments include: Screening instrument, baseline survey, post-intervention survey with client satisfaction questionnaire, and 3 and 6 month follow up surveys to assess outcomes (i.e., any potential sexual victimization experiences, hazardous drinking/changes in drinking). At the beginning of the first in-person session and at the end of the second in-person session three standardized instruments will be administered via individual laptops. These include the Video Vignette Risk Perception Measure (VVRPM) which assesses women's standardized ability to assess sexual assault risk cues. The Adult Faces test from the Diagnostic Analysis of Nonverbal Accuracy 2 (DANVA2) which is used to measure an individual's general ability to sensitivity to perceive nonverbal cues, and the sDERS a measure used to assess state emotion regulation. A copy of all surveys and measures are attached.

10.4 Describe any source records that will be used to collect data about subjects (e.g. school records, electronic medical records).

Response: None

*10.5 Indicate whether or not **individual** subject results, such as results of investigational diagnostic tests, genetic tests, or incidental findings will be shared with subjects or others (e.g., the subject's primary care physician) and if so, describe how these will be shared.*

Response: N/A

*10.6 Indicate whether or not **study** results will be shared with subjects or others, and if so, describe how these will be shared.*

Response:

Study results will be shared with the scientific community through scientific meetings and publications in peer reviewed journals. If requested, findings will be provided to participants at the end of the study in the aggregate.

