17.0 Data Management and Analysis

17.1 Describe the data analysis plan, including any statistical procedures. This section applies to both quantitative and qualitative analysis.

Study 2:

Data Analyses

For the RCT, data will be analyzed according to the intention-to-treat principle [122]. All participants who complete the baseline assessment will be followed (i.e., post-intervention, 3-month and 6-month post-intervention) regardless of treatment participation. Given our experience and past record of retaining participants in longitudinal studies and the relatively brief period of follow-up (6-mos), dropout due to attrition is expected to be low. We anticipate no more than 5% of data will be missing through attrition or wave nonresponse (i.e., not completing all measures at a given time period). To adjust for any missing assessments, we will use multiple imputation procedures [123, 124].

We have three specific hypotheses for the RCT, our analyses are organized below for each hypothesis.

Hypothesis a: Participants in the RPCW intervention will report fewer days of hazardous drinking and improved perception of SRV risk cues on the video risk perception measure (primary outcomes) as compared with participants in the HEC condition.

Differences in relevant outcome variables (e.g., number of heavy drinking days, perception of SRV risk cues) will be tested using a 2 (Condition: RPCW vs. HEC) x 4 (Time: baseline, post-treatment, and 3- and 6-month post-treatment) repeated-measures analysis of variance (RM-ANOVA). The primary effects of interest are the intervention condition main effect and the intervention x time interaction. If a significant condition by time interaction is found, it means that (a) change over time in heavy drinking days differs across intervention conditions and (b) the effect of intervention condition on the outcome is different across time. Therefore, a significant intervention condition by time interaction will be explored by computing the conditional effect of time for each intervention condition and (b) the conditional effect of treatment condition at each of the four time points.

Hypothesis b: Participants in the RPCW intervention will report increased knowledge of safe dating practices and protective behavioral (drinking) strategies (secondary outcomes) compared with participants in the HEC condition.

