Differences in relevant outcome variables (e.g., safe dating practices, protective behavioral drinking strategies) will be tested using the same 2 (Condition) x 4 (Time) repeated-measures analysis of variance (RM-ANOVA) described above for hypothesis a.

Hypothesis c: Participants in the RPCW intervention will report lower rates of SRV as compared with participants in the HEC condition at 6-month post-intervention follow-up.

Given that SRV has a low base rate of occurrence, we consider this hypothesis exploratory and will conduct a preliminary comparison of the incidence of SRV at 3-months and 6-months post-treatment across the RPCW and HEC conditions using a chi-square test.

Effect sizes will be calculated with all analyses in preparation for a Stage II efficacy trial of the intervention.

17.2 If applicable, provide a power analysis.

NOTE: This may not apply to certain types of studies, including chart/records reviews, survey studies, or observational studies. This question is asked to elicit whether the investigator has an adequate sample size to achieve the study objectives and justify a conclusion.

Response:

Study 2:

The sample size of 96 women (48 women per intervention condition) was selected to provide 80% power to detect at least medium effect sizes in RM-ANOVA. For Hypotheses a and b, power calculations were conducted for a 2 (treatment condition) x 4 (time) RM-ANOVA. We calculated power using the following assumptions (1) a sample size of 48 women in each intervention condition (RPCW, HEC), (2) 4 time points for assessment (baseline, post-intervention, and 3- and 6-months post-intervention), (3) a range of correlation values among repeated assessments ($r = .3$ to $.9$), (4) no violation of the sphericity assumption, (5) $\alpha = .05$, two-tailed, and (6) power = 80%. Based on these assumptions, there is 80% power to detect an intervention condition main effect with medium effect sizes ($f = .20$ to $.28$) and both a time main effect and an intervention condition x time interaction with small to medium effect sizes ($f = .05$ to $.21$). For Hypothesis c, statistical power was estimated for a χ^2 test (1 df) of the number of women who were and were not revictimized post treatment by intervention condition (RPCW, HEC). Assuming (1) a total sample of 96 women, (2) $\alpha = .05$, and (3) 80% power, the chi-square analysis can detect a medium effect ($w = .29$) at 3- and 6-month post-intervention.

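### Because baseline is one of four Time levels, the condition main effect estimates only 75% of the mean post-baseline arm difference; a baseline-adjusted post-baseline contrast should replace it

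*Protocol*

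**What the plan says.** Protocol 17.1 (Hypothesis a) and the SAP (Data Analyses) specify a 2 (condition) x 4 (time) RM-ANOVA for heavy drinking days and for the video risk-perception measure. The time levels are baseline, post-treatment, 3 months and 6 months. Two terms carry the hypothesis: "The primary effects of interest are the intervention condition main effect and the intervention x time interaction". Hypothesis b uses the same model.

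Arm differences by visit come second. The plan says that "a significant intervention condition by time interaction will be explored by computing the conditional effect of time for each intervention condition", and then "the conditional effect of treatment condition at each of the four time points"; that set includes baseline. For the next trial, "Effect sizes will be calculated with all analyses in preparation for a Stage II efficacy trial of the intervention".

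Protocol 17.2 and the SAP (Power) assume 48 women per arm, four time points counting baseline, r = .3 to .9, sphericity and two-sided alpha of .05. They claim 80% power for a condition main effect of f = .20 to .28.

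Protocol 10.3 schedules the video measure twice only: "At the beginning of the first in-person session and at the end of the second in-person session three standardized instruments will be administered". Protocol 10.1 gives the same two occasions.

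**The concern.** An intervention cannot act before it is given. With baseline as an ordinary level of Time, the condition main effect averages one visit where the expected arm difference is zero with three visits where an effect can appear. It is a diluted version of the quantity of interest, and its stated power refers to the diluted quantity. Neither document says so, and neither uses baseline as a covariate, which would remove the dilution and also cut the variance.

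Two things are at stake. One is sensitivity at low to moderate correlation. The other is the pilot's stated use: Protocol 1.1 wants initial efficacy data for Stage II power calculations. Both primary terms are tested unconditionally, but only the main effect gives a single signed arm difference, and read as the post-baseline effect it is 25% too small at every r. No post-baseline contrast is named for reporting whatever the result of the interaction test.

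**Working it through.** **Inputs.** From Protocol 17.2 and the SAP: 48 per arm, four visits, r = .3 to .9, sphericity, alpha .05. Assumed: unit SD, equal correlation, independent women, complete data, zero expected baseline difference. Let d be the arm difference in SD units.

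**1. Reproduce the plan.** The variance of a woman's four-visit mean is (1+3r)/4. For a difference d at all four levels, λ = 24d²/[(1+3r)/4] on F(1,94). Power of 80% needs λ ≈ 8.01, so d = 0.398/0.457/0.509/0.556 at r = .3/.5/.7/.9. With f = d/2 this is .199/.228/.254/.278, which matches the stated .20 to .28.

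**2. Main effect when the difference exists only after baseline.** The four-visit average is (0+d+d+d)/4 = 0.75d. Then λ = 0.5625 × 8.01 = 4.51 and power is 55.6% at every r. To restore 80%, d must be 4/3 as large: 0.531/0.609/0.678/0.741 SD. If the difference is at 3 and 6 months only, the average is 0.5d and power is 28.8%.

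**3. Interaction.** λ = 24·Σ(d_t − d̄)²/(1−r) on F(3,282). For (0,d,d,d) the sum is 0.75d², so λ = 18d²/(1−r) = 4.08/7.51/15.52/55.59. For (0,0,d,d) the sum is d². In the plan's metric the first pattern is an interaction f of only .086/.099/.110/.120. Interaction power reaches 80% at r = .61 (first pattern) or .53 (second).

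**4. Either named test.** Under the plan's assumptions the two tests are close to independent. For the three-visit effect, 1 − (1−.556)(1−.360) = .72 at r = .3; likewise .83 at r = .5 and .97 at r = .7. Simulation agrees. At .025 each the figures are .59/.73/.93.

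**5. Baseline-adjusted mean of the three post-baseline visits.** The variance is (1+2r)/3 − r² = (1+3r)(1−r)/3, on F(1,93). At r = .3 it is 1.9 × 0.7/3 = 0.443, so λ = 24 × 0.398²/0.443 = 8.58 and power is 83%.

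Power (%) at the plan's own d, for r = .3/.5/.7/.9:

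| Test | Effect at all three visits | Effect at 3 and 6 months only |
|---|---|---|
| Condition main effect | 56/56/56/56 | 29/29/29/29 |
| Condition x time | 36/62/92/>99 | 47/76/98/>99 |
| Adjusted three-visit mean | 83/93/99/>99 | 49/63/84/>99 |
| Adjusted 3/6-month mean | 73/88/98/>99 | 73/88/98/>99 |

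**6. Does the replacement depend on the time course?** Let D be the mean post-baseline difference. The main effect has λ = 24 × (0.75D)² × 4/(1+3r); the adjusted contrast has λ = 24D² × 3/[(1+3r)(1−r)]. The ratio is 1/[0.75(1−r)] = 1.90/2.67/4.44/13.33. It exceeds 1 for any pattern over visits, because both terms depend on the pattern only through D.

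**7. Video measure.** Two occasions cannot fill a four-level Time factor. Comparing session-2 scores adjusted for session-1 scores has variance 1 − r², and 80% power for 0.55/0.50/0.41/0.25 SD.

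**The case against.** **The power statement is right and the interaction is there to catch divergence.** Both parts stand. A reader might infer that 17.2 is miscalculated, but it reproduces as a four-visit average. A reader might also infer that the trial has 56% power for its primary drinking hypothesis. The documents do not support that, because 56% belongs to one of two named tests and no success rule is stated. Taken together the tests do better, though at r = .3 still only 72% without alpha adjustment, and nothing in the documents narrows r within .3 to .9.

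**A mean contrast is not always better than the interaction.** This also stands. In the late-effect case the interaction beats the three-visit mean at r = .5 and .7 (76/98% against 63/84%). For a fading pattern (d, d/2, 0) it has 33/58/90% at r = .3/.5/.7 against 31/40/60%. So there is no case for demoting the interaction.

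**Making 3 and 6 months the primary contrast is tempting.** The drinking value at the post visit may cover mostly time before the intervention: "They will attend two in-person group intervention sessions about one week apart, and complete two on-line units during the intervening week", and "Immediately following this session, the post-intervention measures, including feedback on the intervention content and process, will be completed". But the look-back of that item is in survey attachments not reproduced in these documents, so the inference cannot be confirmed. If the effect were at post and 3 months only, the 3/6-month mean would have just 25/35/54% power.

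**Selective reporting.** A reader might infer that Stage II inputs will be inflated because by-visit differences follow a significant interaction. That would need planners to use only those estimates. The plan does not say this, and it promises effect sizes with every analysis.

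**It is a pilot.** This lowers the stakes of the power loss. It does not remove the 25% dilution, which does not depend on power.

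**Conclusion.** The point holds as a matter of analysis choice and should be fixed. The condition main effect estimates 75% of the mean post-baseline difference. At the plan's own detectable size its power is about 56% rather than 80% when the difference is sustained over the three later visits. The co-primary interaction covers much of the gap, so the practical loss is material at low to moderate r and small at r of .7 or more. Separately, the video measure as scheduled cannot enter the stated model.

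The figures rest on independent women, equal correlation, complete data and a unit-SD continuous outcome. Sessions are run in groups of up to 8 (Protocol 26.2) and the drinking outcome is a count of days, so the absolute powers are approximate. The 75% needs only a zero expected baseline difference.

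**What to change.** In Protocol 17.1 and the SAP:

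- Replace the condition main effect with one prespecified RPCW-HEC contrast on the mean of the three post-baseline visits, with baseline as a covariate. Estimate and report it with its interval whether or not the interaction is significant.
- Keep condition x time as planned.
- Drop the test of condition at baseline, which is uninformative under randomisation.
- Report the baseline-adjusted 3/6-month mean as a supporting estimate, and state the look-back of the drinking item at each visit.
- Apply the same contrast to the Hypothesis b outcomes.
- For the video measure, compare session-2 scores between arms adjusted for session-1 scores.
- Restate power in 17.2 and the SAP (Power) for these contrasts, for both the sustained and the late effect.

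The cost is a few sentences of wording, with no new data or visits. The reported effect will refer to post-baseline visits rather than a four-visit average, and the three-visit mean has only 49% power at r = .3 if the effect is late.

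### The detectable range f = .05 to .21 for time and condition x time contradicts the no-sphericity-violation assumption listed with it; that assumption gives .05 to .14

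*Protocol*

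**What the plan says.** Protocol 17.2 gives the basis of the power calculation for Hypotheses a and b as six numbered assumptions:

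- "a sample size of 48 women in each intervention condition (RPCW, HEC", so N = 96
- "4 time points for assessment (baseline, post-intervention, and 3- and 6-months post-intervention"
- "a range of correlation values among repeated assessments ($r = .3$ to $.9"
- "4) no violation of the sphericity assumption"
- two-tailed alpha of .05
- 80% power

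From these it derives a detectable condition main effect of f = .20 to .28 and, for the within-subject effects, "both a time main effect and an intervention condition x time interaction with small to medium effect sizes ($f = .05$ to $.21". The Power section of the SAP repeats the same assumptions and ranges. Neither document mentions an epsilon value or a calculation under a sphericity violation.

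Protocol 17.1 (Hypothesis a) states that "The primary effects of interest are the intervention condition main effect and the intervention x time interaction". Its four-point model covers both primary outcomes, hazardous drinking days and the video risk perception measure.

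On the timing of that video measure, Protocol 10.3 says: "At the beginning of the first in-person session and at the end of the second in-person session three standardized instruments will be administered". It continues: "These include the Video Vignette Risk Perception Measure (VVRPM". Protocol 10.1 gives the same two occasions.

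**The concern.** The within-subject range is presented as following from the six assumptions, but its upper end cannot be obtained from them. A value as large as .21 needs a severe sphericity violation, or some other unlisted input, and assumption (4) rules the violation out. The reader cannot tell whether the range or the assumption is misstated.

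The effect concerned is one of the two that the plan calls primary. The trial is also meant to supply data for the power calculation of a Stage II trial, so a sensitivity statement that cannot be reproduced should not be carried forward.

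**Working it through.** **Inputs (Protocol 17.2; same in the SAP).** N = 96 in two arms, m = 4 time points, r = .3 to .9, alpha = .05, power 80%. No sphericity violation means epsilon (e) = 1.

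**Formulas (noncentral F).**

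- Condition main effect: lambda = f² x N x m / (1 + (m − 1)r), df = 1 and N − 2.
- Time and condition x time: lambda = f² x N x m x e / (1 − r), df = (m − 1)e and (N − 2)(m − 1)e. With two arms both effects have the same df, hence the same detectable f.

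**Step 1: reproduce the main-effect range.** With df 1 and 94, 80% power needs lambda = 8.01. N x m = 384.

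- r = .3: f = √(8.01 x 1.9 / 384) = .199
- r = .9: f = √(8.01 x 3.7 / 384) = .278

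This is the printed .20 to .28, so the formulas follow the plan's own convention.

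**Step 2: the within-subject range under assumption (4).** With e = 1 and df 3 and 282, 80% power needs lambda = 11.05.

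- r = .3: f = √(11.05 x 0.7 / 384) = .142
- r = .5: .120
- r = .7: .093
- r = .9: f = √(11.05 x 0.1 / 384) = .054

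The range is .05 to .14. The printed lower end is reproduced and the upper end is not (.21 / .142 = 1.48).

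**Step 3: can .21 arise with e = 1?** At r = 0 the detectable f is .170. At r = −1/3, the lowest common correlation four measures can have, it is .196. So no correlation gives .21 under assumption (4).

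**Step 4: power at f = .21, r = .3.**

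- e = 1: lambda = .0441 x 384 / 0.7 = 24.19, power 99.1%. Simulating the interaction test (4,000 runs) gave 98.8%.
- e = 1/3: lambda = .0441 x 128 / 0.7 = 8.06 on df 1 and 94, power 80.3%.

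**Step 5: what would give the printed ends?**

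| epsilon | f at r = .3 | f at r = .9 |
|---|---|---|
| 1 | .142 | .054 |
| .75 | .157 | .059 |
| .5 | .181 | .068 |
| 1/3 (minimum for four points) | .209 | .079 |

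A value rounding to .21 at r = .3 needs epsilon of .353 or less. A value rounding to .05 at r = .9 needs epsilon of about .93 or more. No single epsilon gives both ends. They match opposite corners of a grid in which epsilon runs from 1 to 1/3, but that is an inference, since the documents give no epsilon.

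**Step 6: the two-point outcome.** With m = 2 sphericity holds trivially, N x m = 192, df are 1 and 94, and lambda is again 8.01.

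- Interaction: √(8.01 x 0.7 / 192) = .171 at r = .3; √(8.01 x 0.1 / 192) = .065 (.0646 unrounded) at r = .9. To two decimals, .06 to .17.
- Main effect: √(8.01 x 1.3 / 192) = .233 at r = .3; √(8.01 x 1.9 / 192) = .282 at r = .9.

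**The case against.** The arithmetic is hard to dispute; the case on the other side concerns consequence, cause and scope.

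- **Little depends on it.** One end of one range is wrong, in a pilot whose sample size is governed by the more demanding condition main effect. The plan's label of small to medium also fits .05 to .14. This stands, and it is why the point is minor.
- **Varied epsilon is not the only possible cause.** With epsilon = 1, requiring 99% power gives .209 at r = .3, and a total of 44 women gives .211. Each gives about .08 at r = .9, so neither explains both ends. A typing error or a figure from another run remains possible. This also stands: the documents prove only that the assumption and the range disagree. Printing .05 to .14 covers those cases.
- **The error is conservative only if assumption (4) is true.** Correct. If epsilon were 1/3 throughout, the range would be .08 to .21 and the printed .05 would be optimistic.
- **The two-point schedule of the video measure is a separate matter and changes the main-effect range too.** The schedule conflict does go beyond sphericity, but it decides which outcomes the printed range can describe, so one clause on scope belongs here. The two-point main effect (.233 to .282) stays within the printed .20 to .28 after rounding.
- **Medium is not defined.** The documents themselves call .20 to .28 medium, and on that label the claim of 80% power for at least medium effects holds. Nothing here tests it against an outside benchmark.

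**Conclusion.** The concern holds and is minor. Under the six listed assumptions the detectable time and condition x time effect is f = .05 to .14, not .05 to .21; the printed upper end is about 48% above the .142 that assumption (4) gives.

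This rests on the noncentral F calculation in the convention that reproduces the plan's main-effect range, a common correlation among the measures, and all 96 women analysed. With 91 women (about 5% fewer) the range is .146 to .055, so allowing for the expected missing data does not explain .21 either.

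If assumption (4) is true, the design detects a smaller interaction than it claims. The choice of N = 96, the main-effect range, and the claim about at least medium effects (on the plan's own label) are unaffected.

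**What to change.** In Protocol 17.2 and in the SAP (Power), make assumption (4) and the range agree, according to the calculation that the sponsor actually ran:

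1. Keep assumption (4) and change the time and condition x time range to f = .05 to .14. This is also the correction if .21 was a typing error or came from another run.
2. If epsilon was in fact varied, keep .05 to .21 and reword assumption (4) to say that epsilon ran from 1 (no violation) to 1/3 (maximal violation for four time points).

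In either case add one clause saying that the range applies to outcomes measured at all four time points. For the video risk perception measure, as scheduled in 10.1 and 10.3, give the two-point interaction range of f = .06 to .17.

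The cost is one reworded range or assumption and one added clause in each document. Sample size, tests, endpoints and visits do not change.
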